# 6.4 Day 14 ( $\pm 2$ days)

- Determination of Ordinal Scale score.
- Review of concomitant medications.
- Review of adverse events.
- Vital signs heart rate, temperature, blood pressure, body weight, oxygenation (use of supplemental oxygen, amount of supplement oxygen used and Sp02 (if possible)) and respiratory rate. Safety Labs if possible, collect blood for bilirubin, creatinine, AST, ALT, hemoglobin, white blood cells, platelet count, absolute neutrophil count, lymphocyte count, plasma or serum glucose, and eGFR.
- If clinical chest imaging (X-ray, CT, MRI) is performed during the subject's participation in the study, results may be obtained.
- Research Labs 15 mL of blood and Collection of Biospecimens for Future Research if possible, additional blood up to 85 mL (minimum of 35 mL) and 40 mL of urine will be collected.

# 6.5 Day 30 (-2 to +7 days)

- Determination of Ordinal Scale score.
- Review of concomitant medications.
- Review of adverse events.
- Vital signs heart rate, temperature, blood pressure, body weight, oxygenation (use of supplemental oxygen, amount of supplement oxygen used and Sp02 (if possible)) and respiratory rate. Collection of most recent (at least within 100 or fewer days) Minimal Data Set (MDS) on record for that participant).
- If clinical chest imaging (X-ray, CT, MRI) is performed during the subject's participation in the study, results may be obtained.

# 6.6 Day 90 (±14 days)

- Determination of Ordinal Scale score.
- Review of concomitant medications.
- Review of adverse events.
- Vital signs heart rate, temperature, blood pressure, body weight, oxygenation (use of supplemental oxygen, amount of supplement oxygen used and Sp02 (if possible)) and respiratory rate. Collection of the most recent Minimal Data Set (MDS) on record for that participant.
- Safety Labs if possible, collect blood for bilirubin, creatinine, AST, ALT, hemoglobin, white blood cells, platelet count, absolute neutrophil count, lymphocyte count, plasma or serum glucose, and eGFR.
- If clinical chest imaging (X-ray, CT, MRI) is performed during the subject's participation in the study, results may be obtained.

# 6.7 Day 180 ( $\pm$ 14 days) - Unblinding

- Determination of Ordinal Scale score.
- Review of concomitant medications.
- Review of adverse events.
- Vital signs heart rate, temperature, blood pressure, body weight, oxygenation (use of supplemental oxygen, amount of supplement oxygen used and Sp02 (if possible)) and

respiratory rate. Collection of the most recent Minimal Data Set (MDS) on record for that participant.

- Safety Labs if possible, collect blood for bilirubin, creatinine, AST, ALT, hemoglobin, white blood cells, platelet count, absolute neutrophil count, lymphocyte count, plasma or serum glucose, and eGFR.
- If clinical chest imaging (X-ray, CT, MRI) is performed during the subject's participation in the study, results may be obtained.

# 7 Study Procedure Details

#### 7.1 Assessments

Study staff will obtain relevant information pertaining to physical examinations/assessments by communicating with nursing home staff and abstracting information from the subject's nursing home charts and Minimal Data Sets (MDS).

### 7.2 SARS-CoV-2 Testing

Subject must have a SARS-CoV-2 infection confirmed by PCR test at Mayo Clinic or other CLIA certified laboratory prior to randomization. A SARS-CoV-2 test may be ordered for research purposes after research consent is obtained. During the influenza season, a rapid influenza and RSV test will also be obtained at a Mayo Clinic or other CLIA certified laboratory.

### 7.3 Determination of Ordinal Scale

The subject's score on the Ordinal Scale for Clinical Improvement (Appendix 1) will be recorded daily (if feasible) through day 14 using the subject's worst assessments of the day. In addition, the score will be recorded on days 30, 90 and 180, if possible.

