## 2 Study Objectives

#### 2.1 Primary Objectives

The primary objective is to test the efficacy of the senolytic drug (Fisetin) in preventing or delaying progression of CoV severity in nursing home patients with proven CoV according to a 7 point scale for nursing home CoV severity adapted from the WHO Ordinal Scale for Clinical Improvement of CoV\*:

- Not hospitalized nor on additional oxygen (compared to baseline), at baseline level of function (as assessed by activities of daily living).
- Not hospitalized nor on additional oxygen, but below previous level of function.
- Hospitalized or moved to a more intensive unit within the nursing home because of additional dysfunction (not simply because of positivity), but not requiring additional oxygen nor placed on an antiviral drug for worsening CoV symptoms.
- Hospitalized or moved to a more intensive unit within the nursing home and requiring additional oxygen (vs. baseline) and/ or placed on an antiviral drug for worseningCoV symptoms.

- Hospitalized or moved to a more intensive unit within the nursing home and requiring additional oxygen by ECMO or ventilator.
- Transferred to palliative care to provide end-of-life care.
- Death.

\*The WHO Ordinal Scale for Clinical Improvement of CoV (Appendix 1) is scored from 0 to 8 with 0 = no evidence of infection to 8 = death. Our adapted scale does not include scores 0 or 1, since no subjects in COVID-FIS will meet these criteria (e.g., all subjects have proven CoV infection, so none have "no infection").

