# **Appendix 1.** Ordinal Scale

# **Ordinal Scale for Clinical Improvement**

Patient State	Descriptor	Score	
Uninfected	No clinical or virological evidence of infection	0	
Ambulatory	No limitation of activities	1	
	Limitation of activities	2	
Hospitalized Mild disease	Hospitalized, no oxygen therapy	3	
	Oxygen by mask or nasal prongs	4	
Hospitalized Severe Disease	Non-invasive ventilation or high-flow oxygen	5	
	Intubation and mechanical ventilation	6	
	Ventilation + additional organ support – pressors, RRT, ECMO	7	
Dead	Death	8	

https://www.who.int/blueprint/priority-diseases/key-action/COVID-19 Treatment Trial Design Master Protocol synopsis Final 18022020.pdf

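### Section 7.3 sends the ordinal score to the WHO 0–8 table in Appendix 1 instead of the 7-level list in Section 2.1, and that list has no level for additional oxygen given without a transfer

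*Combined protocol and SAP*

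**What the plan says.** Section 7.3 is the only place that says how the score is obtained: "The subject's score on the Ordinal Scale for Clinical Improvement (Appendix 1) will be recorded daily (if feasible) through day 14". For a day with more than one assessment, the section also gives a rule for choosing among them: "using the subject's worst assessments of the day". The visit lists in Section 6 and the schedule in Appendix 2 name the ordinal scale without defining it.

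Appendix 1 carries the title used in 7.3 and prints one table, with scores 0 (uninfected) to 8 (dead). The footnote to Section 2.1 describes it the same way: "The WHO Ordinal Scale for Clinical Improvement of CoV (Appendix 1) is scored from 0 to 8". The footnote then adds: "Our adapted scale does not include scores 0 or 1".

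The adapted scale is listed only in Section 2.1, as seven unnumbered bullets, counted here as levels 1 to 7. Level 2 is "Not hospitalized nor on additional oxygen, but below previous level of function". Level 3 is hospitalization or a move to a more intensive unit "because of additional dysfunction (not simply because of positivity), but not requiring additional oxygen". Level 4 begins "Hospitalized or moved to a more intensive unit within the nursing home and requiring additional oxygen (vs. baseline" and offers an antiviral for worsening symptoms as an additional or alternative criterion. Level 5 is hospitalization or a move with ventilator or ECMO oxygen, level 6 is palliative transfer and level 7 is death.

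The Study Summary and Sections 3.4, 8.1 and 8.2 all use the 7-point scale. Section 3.4 cites Appendix 1 and Section 2 together.

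**The concern.** There are two separate defects in the definition of the primary outcome.

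(a) Staff who follow 7.3 as written arrive at the WHO table, not at the scale on which the trial is powered and tested. The error would be hard to see in the data. The footnote removes WHO scores 0 and 1, and the remaining scores, 2 to 8, also number seven, so a stored WHO score could pass as the 7-point score.

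(b) Even with the correct list in hand, one state has no level: additional oxygen, above baseline, given where the resident already is. Sites would score it by habit or leave it blank. If the level were chosen after unblinding, it would be a data-dependent decision on the primary endpoint.

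**Working it through.** **1. The two scales side by side.**

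| Feature | WHO table (Appendix 1) | List in Section 2.1 |
|---|---|---|
| Number of scores | 9 (0–8); 7 remain after dropping 0 and 1 | 7 |
| Palliative care | no level | level 6 |
| Move to a more intensive nursing-home unit | no level | levels 3–5 |
| Antiviral for worsening symptoms | not a criterion | levels 3 and 4 |
| Function compared with baseline | no | separates levels 1 and 2 |
| Ventilation and organ support | scores 5, 6 and 7 | level 5 |

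A WHO score therefore does not determine a 2.1 level. WHO 2–8 is not the 2.1 list under other numbers either. WHO score 1 is a patient without limitation of activities, which the footnote says no subject will meet, yet 2.1 level 1 is a resident at baseline function, and Section 3.5 includes residents with no symptoms.

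**2. Coverage of the 2.1 list.** Take living, non-palliative residents and cross four factors: location (in place, or hospitalized/moved), additional oxygen (none, simple, ventilator/ECMO), antiviral for worsening symptoms (no, yes) and function (baseline, below). This gives 2 × 3 × 2 × 2 = 24 combinations. Two coding assumptions are made: every hospitalization or move is due to additional dysfunction, and ventilator/ECMO oxygen by itself counts only under level 5.

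- In place, no additional oxygen: 4 combinations, each matching one level.
- In place, additional oxygen: 8 combinations, none matching any level. Four involve simple oxygen; the four with ventilator/ECMO are unlikely in practice.
- Hospitalized or moved: 12 combinations, each matching at least one level. Two of them (ventilator/ECMO plus antiviral) literally match both level 4 and level 5.

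The WHO table does not fill the gap, because its entry "Oxygen by mask or nasal prongs" stands under hospitalized patients.

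**3. The plan's own power figure.** Inputs from Section 8.1: 75 per group, two-sided alpha 0.05, controls spread equally (1/7 per level), log odds ratio 0.81. The formula for a proportional-odds comparison with 1:1 allocation is N = 12(z₀.₉₇₅ + z₀.₈₀)² / [θ²(1 − Σp̄ᵢ³)], where θ is the log odds ratio and p̄ᵢ is the mean of the two arms' probabilities. Here Σp̄ᵢ³ = 0.0240, so N = 12 × (1.960 + 0.842)² / (0.6561 × 0.9760) = 147.1, against 150 planned. Power at 150 is Φ(0.81 × √(150/12 × 0.9760) − 1.960) = Φ(0.869) = 80.8%. The stated 80% is reproduced. With 7, 8 or 9 equally filled levels the power is 80.8%, 81.0% and 81.1%, so the different number of levels does not affect the sample size.

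**4. Size of the oxygen gap.** The documents give no frequency, so the counts below are assumptions. Power is approximated by Φ(|Z|/√V − 1.96), where Z and V are the proportional-odds score statistic and its variance at the expected counts, with odds ratio 2.25. The Fisetin probabilities for levels 1 to 7 are 0.273, 0.201, 0.154, 0.122, 0.099, 0.082 and 0.069. The base case is |Z| = 9.690 and V = 12.200, so power = Φ(2.774 − 1.96) = 79.2%. Level 4 is expected to hold 75/7 + 75 × 0.1221 = 10.71 + 9.16 = 19.87 residents. The affected residents are taken from level 4 in proportion from both arms; this choice is only for illustration.

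| Affected residents | Left unscored | Scored level 3 | Scored level 2 |
|---|---|---|---|
| 3 of 150 (15% of level 4) | 79.1% | 79.0% | 78.3% |
| 15 of 150 (75% of level 4) | 78.4% | 78.6% | 74.7% |

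A simulation of 60,000 trials shows the same pattern. Base power is 80.3%; it is 79.3% with 3 residents scored level 2 and 75.7% with 15 scored level 2. The 79.2% base is a feature of the approximation and not a finding against the plan.

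No power figure is given for defect (a), because no conversion between the scales exists.

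**The case against.** The strongest reply is that (a) is a cross-reference slip. The Study Summary and Sections 2.1, 3.4, 8.1 and 8.2 all name the 7-point scale, and in most of those places the appendix is cited as the parent scale. A correctly built CRF would make the slip harmless. This stands as far as it goes: the intent is clear and the CRF is not available. A reader might infer that the trial stored WHO scores as its primary outcome; the documents do not show that. However, clear intent in the analysis sections does not correct the recording instruction, and no stated intent fills the oxygen gap, which remains even if the CRF copies 2.1 exactly.

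A second reply is that the gap may be rare. Entry on up to 2 L of oxygen (Section 4.1) is weak evidence for it, because the scale counts only oxygen above baseline. Better evidence is that Section 3.1 lists an increase in oxygen requirement as an item separate from transfers to another unit, hospital or ICU. That makes the state possible but does not say how common it is.

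A reader might also infer that any wrong scores can be fully rebuilt, since Section 5.2.2 says that concurrent therapies, including oxygen, will be recorded. The documents do not support that either. Section 3.1 makes daily recording of oxygenation status, medication use, unit moves, palliative care and physical function subject to feasibility or to chart abstraction. The Minimal Data Set, which carries functional status, is scheduled at baseline and Days 30, 90 and 180, but not at Day 14. The boundary between levels 1 and 2 is therefore the part most likely to be lost.

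**Conclusion.** Both defects hold on the text. The scoring instruction points to a table that is not the primary endpoint scale and cannot be converted to it. The list that is the endpoint scale leaves one possible state without a level and gives two levels to another. Whether any outcome was actually mis-recorded is unknown, and no such claim is made.

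The numerical effect is small. With 3 affected residents the loss is about 1 percentage point or less. Only an extreme assumption, with about three quarters of expected level-4 residents affected and all scored two levels too mild, costs 4.5 points (79.2% to 74.7%). These figures rest on the equal control distribution of Section 8.1, proportional odds and assumed counts. A reader might take them as a shortfall against the planned 80%; they are not, because the plan's own figure reproduces at 80.8%.

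The matter should be fixed because it concerns the definition of the primary outcome, and scoring left to each site's habit cannot be defended after unblinding.

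**What to change.** 1. Print the seven Section 2.1 levels, numbered 1–7, in Appendix 1 and on the CRF. Point Section 7.3 and the Section 6 visit lists to them.
2. Clarify the 2.1 footnote so that WHO scores 2–8 cannot be read as the 7-point scale.
3. Before unblinding, the sponsor assigns a level, for outcome scoring only, to additional oxygen given without hospitalization or a unit move.
4. Extend the existing worst-of-the-day rule in 7.3 to say that the highest applicable level counts, so that each resident has exactly one level, including those on ventilator/ECMO plus an antiviral.
5. Only if WHO scores were recorded: re-derive the 7-point score, blinded to treatment, from existing oxygen, medication, location, palliative-care and function records, and report how many scores cannot be recovered, with the level 1/2 boundary shown separately.

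Items 1 to 4 cost protocol and CRF wording and one documented scoring decision. Item 5 costs a blinded record review and may be incomplete. No new assessments and no change to patient care are needed.

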# 7.4 Safety Labs

Safety labs should be collected and assessed within 48 hours prior to randomization: bilirubin, creatinine, AST, ALT, hemoglobin, white blood cells, platelet count, absolute neutrophil count, lymphocyte count, plasma or serum glucose, and eGFR. If possible, safety labs will also be collected at the other time points listed in Appendix 2. Results from laboratory testing performed as part of nursing home care may also be obtained.

Treatment-emergent AEs and laboratory abnormalities will be summarized using descriptive statistics and listed by subject.

#### 7.5 Research Labs

If possible, at each of the time points listed Appendix 2, 15 ml of blood will be collected to measure p16INK4A positive CD3+T lymphocytes - a biomarker of senescence and chronological aging. Blood will be tested for the CoV N and S1 antibodies by ELISA. The N antibody, if positive, indicates a past infection with CoV and is not affected by the RNA vaccines. The S antibody can become positive due to past CoV infection or CoV RNA vaccination. This will allow us to test both response to the vaccine in those subjects who are vaccinated as well as verifying previous infection/ adequate immune response to CoV infection. As is the case for MCL (Mayo Clinic Labs), samples will be handled in BSL-2 conditions.

# 7.6 Biospecimens for Future Research

If possible, at each of the time points listed Appendix 2, up to 40 ml of urine and up to 85 ml of blood will be collected and stored for future research. The goal will be to evaluate and answer pertinent questions related to the biology of CoV infection in the elderly, aging, and senescence. Studies utilizing these samples will allow us to gain a greater understanding of the pathophysiology pathophysiology of CoV infection in the elderly, accelerated aging, and the potential for us to develop new therapies to improve patient outcomes.

# 8 Statistical Plan

### 8.1 Sample Size Determination

Power calculations for the comparison of the Fisetin and control groups were made assuming an equal distribution among the 7-point scale categories at Day 14 among the controls using a two-sided significance level of 0.05 (alpha). With 75 subjects per group, the study would have 80% power to detect a log odd's ratio of 0.81 which translates to an odd's ratio of 2.25 comparing the control to Fisetin group. Power calculations were run using the PASS software package.

#### 8.2 Statistical Methods

All participants who are randomized will be included in the primary efficacy analysis. The analysis will follow the ITT principle (*i.e.* according to the treatment arm they are randomized to). For the primary analysis using the values of the 7-point scale, we will test the coefficient of the treatment effect (as a fixed effect) in an ordinal logistic regression model using a 2-sided 0.05 level Wald test after adjusting for key baseline variables such as baseline COVID severity status, age, and sex that show imbalance between the groups. Subjects who withdraw early but received at least some treatment will have their last known values carried forward until they complete the study at Day 180±14. All participants who receive any dose of drug (Fisetin or placebo) will be included in the safety and tolerability evaluation. The definitions of adverse events are described in Sections 9.1-9.3. Participants will be assessed over the entire period of drug administration. Frequency tables will be generated to summarize the occurrence of AE's by treatment arm. Comparisons of the rates of individual AEs will be done using tests of proportions such as the Fisher's exact test or Chi-squared test.

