## 3 Study Design

#### 3.1 General Description

This study is a pilot, randomized, placebo-controlled, multi-site study of Fisetin in elderly nursing home participants. A total of 250 participants will be enrolled in this study. Study staff and participants will be blinded with regards to groups. Subjects will be randomized to placebo or treatment. Fisetin 20 mg/kg/day or placebo will be made available by the study staff for oral or enteral administration on study Days 0, 1, 8, and 9.

If Remdesivir or another anti-viral agent or immunization should become standard of care in nursing home CoV patients (*e.g.*, approved by the FDA) during the study, patients being treated with such agents may be enrolled, with randomization stratified based on whether subjects are on such an anti-viral agent. We conducted studies of mice (N=6 old mice; age 22.9±0.7 months [means±SEM]; females) on higher doses of Fisetin than to be administered here (100 mg/ kg/ day for 2 days) by gavage and Remdesivir (50 mg/ kg/ day) i.p. We did not find Fisetin plus Remdesivir resulted in increased toxicity (changed body weight, food intake, activity, grooming, appearance, or frailty score) during any of the 4 days following administration *vs.* Remdesivir alone (Table 3; 100 mg/ kg/ day for 2 days by gavage; N=6 old mice; age 23.4±0.7 months). Therefore, if patients already in COVID-FIS are started on Remdesivir, they will not be withdrawn from the study. During statistical analyses, patients will be analyzed regarding Remdesivir administration *post hoc.* 

Table 3. Remdesivir + Fisetin is Not More Toxic than Remdesivir Alone

Treatment	Age (Mo.)	Frailty Score	Body Wt. (g)	Body Temp. (°C)	Body Wt. (g)	Frailty Score	Body Wt. (g)	Body Temp. (°C)	Body Wt. (g)
Date	5/4	5/4	5/4	5/4	5/9	5/10	5/10	5/10	5/11
RDV+Fisetin	25.03	0.357	27.2	31	26.00	0.37	25.7	31.73	26.1
RDV+Fisetin	22.20	0.125	34.2	32	34.9	0.185	33.8	32.07	34.1
RDV+Fisetin	22.35	0.143	30.1	32	28.5	0.259	27.6	32.83	28.2
RDV+Fisetin	19.47	0.21	29.5	32	27.3	0.278	27.6	31.9	27.8
RDV+Fisetin	24.18	0.20	42.2	32	41.5	0.204	39.8	30.9	39.7
RDV+Fisetin	24.18	0.161	28.3	31.7	27.9	0.204	27.9	32.17	28.3
Mean	22.90	0.2	31.9	32	31.02	0.25	30.4	31.93	30.7
SEM	0.752	0.031	2.08	0.14	2.24	0.026	2.00	0.24	1.93
RDV	24.01	0.214	27.6	31.7	27.1	0.241	26.6	31.67	26.8
RDV	23.59	0.232	27.9	32.1	27.9	0.296	27.8	32.6	28
RDV	22.20	0.268	30.9	31.6	29.9	0.241	29.1	32.3	29.3
RDV	22.20	0.125	34.5	32.4	34.1	0.185	33.8	32.77	33.5

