# 5.3 Method for Assigning Subjects to Treatment Groups

Subjects will be randomized to either Fisetin or placebo using an internet-based, web browser randomization procedure maintained by the data management team at Wake Forest School of Medicine. Study coordinators access the randomization application through the trial website. Access to this application is password-protected and its communications are encrypted. Once security requirements are satisfied, consent and eligibility of the participant are verified, and randomization will occur. Randomization is controlled centrally based on each potential participant's consent and eligibility status. ONLY eligible participants will have the randomization button displayed. It will be impossible to randomize an ineligible person, or a person for whom screening or consent is incomplete. We will use a permuted block randomization scheme with varying block sizes and without stratification so that group assignment is balanced as the study proceeds, but study personnel will not be able to predict treatment assignment.

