# 6.1 Screening Visit (Days -2 to 0)

Patients will be pre-screened prior to being recruited for the study. Subjects will be screened within 3 days before randomization to determine eligibility for participation in the study.

Written informed consent will be obtained from the nursing home resident or from a Legally Authorized Representative (LAR) who can provide informed consent. Sections B to E (B: Hearing, Speech, and Vision, C: Cognitive Patterns, including the Brief Interview for Mental Status, D: Mood, and E: Behavior) of the most recent (within the last 100 days) Minimum Data Set (MDS) will be utilized to determine participants' ability to provide a truly informed consent and such an ability should be verified by staff with access to the nursing homes (e.g., Medical or Nursing Director, nurse practitioner, physician's assistant) and if the participant is not able, their LAR will be asked. All MDS datasets for each subject will be collected throughout their inclusion in the study (up to 194 days) and the date(s) and type of vaccinations for CoV will be recorded.

In the pandemic situation where access to nursing homes and hospitals is limited, if allowed, digital/electronic consent will be obtained from the patient's LAR and will be documented by the investigator or the authorized designee. For any subject, it is the responsibility of the investigator or study team member to obtain consent prior to performing any protocol-mandated assessment.

After the informed consent and agreement by the patient's nursing home attending physician, nurse-practitioner, or physician's assistant, the following assessments are performed to determine eligibility requirements as specified in the inclusion and exclusion criteria. Assessments performed as part of the routine care of the subject by nursing home staff may be used to assess eligibility.

- Demographics.
- Focused medical history including the following information if feasible: date of first symptoms, overall symptoms, exposure source, demographics, baseline characteristics, allergies, medical history, reasons for nursing home admission (diagnoses, key symptoms and signs at and since admission as abstracted from the most recent MDS or available nursing home records).
- Determination of Ordinal Scale score.
- Review of concomitant medications including any COVID-19 vaccinations.
- Review of adverse events.

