- Influence of demographic factors on outcomes: These endpoints of interest will tie in with earlier stated analyses, where we will overall assess how these demographic factors such as age, biological sex, and race and ethnicity may influence the outcomes. Since this study will be done at multiple different nursing homes that see different races and ethnicities of patients, these analyses can help to assess if there are any differential outcomes or interactions with factors on these outcomes.
- Senescent cell markers: The distribution of changes in the senescent cell markers will be summarized graphically stratified by treatment arms. Differences between the groups will be assessed using linear regression analysis at the time of interest, adjusting for baseline values. Mixed effects models, where feasible, will also be used to assess the treatment affect using all available measurements.

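### The primary ordinal model adjusts only for covariates found imbalanced, with no criterion and an open list; always adjusting for baseline severity would gain power at no cost in patients if that score is prognostic.

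*Combined protocol and SAP*

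**What the plan says.** Section 8.2 (Statistical Methods) specifies a two-sided 0.05 Wald test of the treatment coefficient in an ordinal logistic regression, "after adjusting for key baseline variables such as baseline COVID severity status, age, and sex that show imbalance between the groups". The available text gives no threshold or test for imbalance, no final covariate list and no coding.

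Section 8.1 powers the trial without covariates, "assuming an equal distribution among the 7-point scale categories at Day 14 among the controls": "With 75 subjects per group, the study would have 80% power to detect a log odd's ratio of 0.81", which it converts to an odds ratio of 2.25.

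Three other places bear on this:

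- Section 6.1 lists "Determination of Ordinal Scale score" at screening. Section 6.2 and Appendix 2 schedule it again at Day 0.
- For the senescent cell markers, the analysis plans for secondary endpoints set no imbalance condition: "Differences between the groups will be assessed using linear regression analysis at the time of interest, adjusting for baseline values".
- Section 5.3 states: "We will use a permuted block randomization scheme with varying block sizes and without stratification". The design therefore does not balance severity between arms. Section 3.1, however, foresees enrolling patients on an antiviral that becomes standard of care, "with randomization stratified based on whether subjects are on such an anti-viral agent".

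**The concern.** Observed imbalance is the wrong trigger. In a randomised trial it is chance, whereas the value of a covariate lies in how well it predicts the outcome. A strongly prognostic score that happens to be balanced would be left out, and its precision lost.

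The rule is also not reproducible. With no criterion and an illustrative list, the covariates can be settled after the baseline table is seen. The severity variable is not pinned down either: it could be the ordinal score or the symptom grade used in section 4.1. (Section 3.5 refers to a Table 4 for symptom severity that is not in the text available to me.)

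Finally, an odds ratio from a proportional-odds model changes meaning when a prognostic covariate enters. Chance imbalance would thus decide whether the reported figure is marginal or conditional, and whether it is comparable with the 2.25 used for planning.

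**Working it through.** **1. The planned power.** Inputs from 8.1: 75 per arm (N = 150), two-sided alpha 0.05, odds ratio 2.25 (log 0.811), seven equally likely control categories. Whitehead's formula is V = (N/12)(1 − Σp̄³), with power = Φ(|log OR|·√V − 1.96), where p̄ is the category share averaged over the arms.

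- 1 − Σp̄³ = 0.976, so V = 12.5 × 0.976 = 12.20 and √V = 3.493.
- Power = Φ(0.811 × 3.493 − 1.96) = Φ(0.87) = 80.9%.

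The stated 80% is right as an unadjusted figure. Unadjusted power of 90% would need about 99 per arm.

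**2. How often severity would enter the model.** The standardised mean difference (SMD) in baseline score has standard error √(2/75).

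- SMD above 0.10: 2[1 − Φ(0.10 × √37.5)] = 2[1 − Φ(0.612)] = 54% (53 to 56% in simulation).
- Baseline test at p<0.05: about 5%.
- Baseline test at p<0.20: 19 to 20%.

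The same sentence therefore allows severity to be in the model in anything from one trial in twenty to more than half.

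**3. Power by rule.** Simulation with 6,000 trials per scenario, 75 per arm, seven equal control categories at Day 14 and a proportional-odds Wald test at 0.05. The conditional effect was solved so that the unadjusted odds ratio stays at 2.25, so unadjusted power is 80% throughout. The baseline distributions and correlations are assumptions. Monte Carlo standard error is about 0.5 points.

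| Baseline score | Rank correlation with Day 14 | Always adjust | Adjust if p<0.05 | Adjust if SMD>0.10 |
|---|---|---|---|---|
| Four levels (45/30/10/15%) | 0 | 80.0% | 80.0% | 80.1% |
| Four levels | 0.25 | 82.9% | 80.0% | 81.7% |
| Four levels | 0.50 | 91.5% | 81.1% | 87.6% |
| Four levels | 0.65 | 97.1% | 81.6% | 92.2% |
| Two levels, 85/15% | 0.19 | 81.6% | 80.0% | 81.0% |
| Two levels, 85/15% | 0.35 | 85.5% | 80.4% | 83.7% |
| Two levels, 70/30% | 0.25 | 82.6% | 80.1% | 81.6% |
| Two levels, 70/30% | 0.46 | 89.3% | 81.1% | 86.3% |

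Forcing in age and sex when neither is prognostic costs at most 0.2 points.

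**4. Cross-checks.** A separate simulation (4,000 trials per setting, 40/30/20/10% baseline, r the correlation with the latent Day 14 outcome) gave, unadjusted against always adjusted: 81.8% and 81.6% at r = 0; 79.4% and 84.0% at 0.3; 81.5% and 92.1% at 0.5; 79.6% and 98.3% at 0.7. The p<0.05 rule gave 82.4% at r = 0.5. Dividing the residual variance by 1/(1 − r²) gives a rough check: at r = 0.5, Φ(0.81 × 3.493/√0.75 − 1.96) = Φ(1.31) = 90.4%, equivalent to 75/0.75 = 100 per arm unadjusted.

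**5. Type I error.** In the main simulation it is 3.3 to 5.3% under the mechanical rules and 5.1 to 5.4% when always adjusting (standard error about 0.3 points). As an upper bound on an open choice, taking the most favourable of the eight subsets of severity, age and sex gives 8.2% (correlation about 0.25) to 9.6% (about 0.50).

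**6. The odds ratio.** With the unadjusted value at 2.25, the conditional odds ratio for the four-level baseline is 2.33, 2.66 and 3.17 at correlations 0.25, 0.50 and 0.65.

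**The case against.** The strongest reply is that the large gains rest on the less likely scenarios. Section 2.1 scores each resident against that resident's own baseline and section 4.1 limits severity at entry, so Day 0 scores may cluster low. In the clustered scenarios the gain over the p<0.05 rule is 1.6 to 8.2 points, and over the SMD rule 0.6 to 3.0. The upper ends assume two log-odds per level, an odds ratio of about 7.4. This stands: 10 to 15 points is the top of a range and not an expectation.

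It is also true that no validity failure follows from the rule as written. Choosing covariates from a baseline table does not use outcomes, so the 8.2 to 9.6% figure bounds a misuse that the text does not describe.

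A third point is that section 7.3 ties the recorded score to Appendix 1, the 0 to 8 WHO scale, while the endpoint is the adapted 7-point scale. That ambiguity affects the Day 14 endpoint equally; using the same scale at both times resolves it for the covariate. Section 7.3 also takes the day's worst assessment, and section 6.2 asks for pre-dose assessment only where feasible, so the covariate must be defined as a pre-dose score.

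The contrast with the marker analysis is only suggestive, because adjustment in a linear model does not shift the estimand in the same way. None of this supplies the missing criterion or favours chance imbalance as the selector.

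**Conclusion.** The concern holds. The covariate set of the primary test is not fixed, and its selection rule discards precision that the trial could have without extra patients. The planned 80% is correct and is kept under the present wording, and a mechanical rule does not inflate type I error. This is therefore a matter of efficiency and pre-specification that should be corrected, not a flaw that invalidates the test.

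Against a p<0.05 rule, always adjusting gains nothing if baseline severity is not prognostic, about 1.5 to 3 points at a correlation of 0.2 to 0.25, about 10 at 0.50 and 15 at 0.65. Where severity is prognostic, the gain against an SMD>0.10 rule is about 0.6 to 5 points. The size depends on the baseline distribution and correlation, neither of which the documents give. The case for fixing the covariates in advance does not depend on them.

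**What to change.** In section 8.2, remove the wording that makes the covariate list illustrative and the clause that makes entry depend on imbalance. State instead:

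- The primary model always contains treatment, the baseline 7-point score, age and sex, whatever the observed balance.
- The baseline score is the last one before the first dose, on the same adapted scale as the endpoint, entered as one linear term. Add a short rule for a missing value.
- The primary odds ratio is conditional on these covariates, and the unadjusted model is reported as a sensitivity analysis.

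Separately, reconcile sections 3.1 and 5.3 on stratification by antiviral use, and add baseline antiviral use to the model only if randomisation is stratified by it.

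The cost is a short amendment to 8.2 before unblinding. No new visit is needed, since the score is already scheduled at screening and Day 0. The one downside is interpretive: at a correlation of 0.50 the reported odds ratio would be about 2.7 where the unadjusted one is 2.25. That is a different estimand, not a larger effect, and the report should say so.
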